6.6.4 Dose adjustment/dose delay

Dose adjustment and/or cycle delay are permitted in case of adverse reaction. In case of toxicity, cycle delays and dose modifications should be implemented according to Appendix 4 ([Section 10.4](#)). Every effort will be made to administer the full dose regimen and maximize dose intensity.

Dose adjustments will be made according to the worst grade of adverse reaction observed within a cycle. If a participant experiences several adverse reactions and there are conflicting recommendations, the most conservative dose adjustment recommended should be followed.

Administration of the study treatment will be discontinued in the event of a TEAE that persists despite appropriate dose modifications or any other AE that, in the opinion of the Investigator, warrants discontinuation.

Pembrolizumab, ramucirumab or tusamitamab rvtansine can be discontinued prematurely. The patient will remain on study treatment until the last IMP can be discontinued until disease progression, unacceptable AE, or the participant's or investigator's decision to stop the treatment. The reason for premature discontinuation will be captured in the appropriate eCRF page.

Dose modifications different from those stated in the protocol should be made only in consultation with the Sponsor unless required for immediate participant safety.

All changes to study treatment administration must be recorded in the eCRF.

In the event of neutropenia, therapeutic G-CSF should be administered according to the current American Society of Clinical Oncology (ASCO) guidelines ([23](#)). In case of neutropenia or febrile neutropenia, prophylactic G-CSF should be started and in case of second episode beside prophylactic G-CSF, then dose should be reduced.

The acceptable treatment window for tusamitamab rvtansine and ramucirumab and pembrolizumab administration is ± 2 days for a Q2W (doublet cohort) and ± 3 days for a Q3W administration (triplet cohort).

See Appendix 4 in [Section 10.4](#) for further guidance in dose modification or discontinuation. Approved product label should be followed for patient receiving ramucirumab treatment for supportive care and dose modification requirement due to not listed adverse events. During the conduct of the study, second dose reduction may be needed, and need to be decided case by case discussion with the sponsor.

In case a dose reduction is necessary, the study intervention will be administered as shown in [Table 11](#) and [Table 12](#):

Table 11 - Dose modification for toxicity in doublet cohort

Drug name	Starting dose	1 st dose reduction	2 nd dose reduction
tusamitamab rvtansine	100 mg/m ² Q2W	80 mg/m ² Q2W	(not permitted)
ramucirumab	8 mg/kg Q2W	6 mg/kg Q2W	5 mg/kg Q2W

Table 12 - Dose modification for toxicity in triplet cohort

Drug name	Starting dose	1st dose reduction	2nd dose reduction
tusamitamab rfvansine	150 mg/m ² Q3W	120 mg/m ² Q3W	(not permitted)
ramucirumab	10 mg/kg Q3W	8 mg/kg Q3W	6 mg/kg Q3W
pembrolizumab	200 mg Q3W	(not permitted)	(not permitted)

Any patient who requires a tusamitamab rfvansine or ramucirumab dose reduction will continue to receive a reduced dose until discontinuation from tusamitamab rfvansine/ramucirumab/pembrolizumab or discontinuation from the study.

Any patient who has had 1 tusamitamab rfvansine dose reduction or 2 ramucirumab dose reductions and who experiences an event that would cause an additional dose reduction must be discontinued from tusamitamab rfvansine/ramucirumab.

If 1 of the 3 drugs (tusamitamab rfvansine or ramucirumab or pembrolizumab) is prematurely permanently discontinued, the other drug(s) can be continued until disease progression.

Retreatment of a patient requiring a dose delay of more than 1 month will need to be justified by an individual case risk-benefit assessment.

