Peripheral neuropathy	Grade 1: Asymptomatic	Administer ramucirumab as planned,	Administer tusamitamab rfvansine as planned,	Patient who has ongoing Grade 1 neuropathy has high risk of worsening of his/her symptoms and should be closely followed.
	Grade 2: Moderate symptoms; limiting instrumental Activities of Daily Living	Delay cycle until recovery to ≤ Grade 1; at next cycle, administer ramucirumab as planned,	Delay cycle until recovery to ≤ Grade 1 and dose reduction if no improvement with dose delay	
	Grade 3: Severe symptoms; limiting self care Activities of Daily Living	Administer ramucirumab as planned,	Definitive discontinuation of tusamitamab rfvansine	
	Grade 4: Life-threatening consequences; urgent intervention indicated	Administer ramucirumab as planned,	Definitive discontinuation of tusamitamab rfvansine	
Neutrophil count decreased	Grade 1 <LLN - 1500/mm ³ ; <LLN - 1.5 × 10 ⁹ /L	No change in IMPs administration.	No change in IMPs administration	No intervention.
	Grade 2 <1500 - 1000/mm ³ ; <1.5 - 1.0 × 10 ⁹ /L	Delay the cycle until recovery of absolute neutrophil count >1500/mm ³ . Restart at the same dose.	Delay the cycle until recovery of absolute neutrophil count >1500/mm ³ . Restart at the same dose.	No intervention.
	Grade 3 <1000 - 500/mm ³ ; <1.0 - 0.5 × 10 ⁹ /L Or Grade 4 <500/mm ³ ; <0.5 × 10 ⁹ /L	Delay the cycle until recovery of absolute neutrophil count >1500/mm ³ . Restart when absolute neutrophil count >1500/mm ³ at the same dose. Prophylactic G-CSF should be considered in all subsequent cycles	Delay the cycle. Restart the treatment when absolute neutrophil count >1500/mm ³ at the same dose prophylactic G-CSF can be considered in all subsequent cycles	Follow ASCO guidelines on usage G-CSF and antibiotherapy (20, 23). Repeat test every 3 days.
	Grade 4 >7days <500/mm ³ ; <0.5 × 10 ⁹ /L	Delay the cycle until absolute neutrophil count >1500/mm ³ . 1st episode administer next cycle with ramucirumab at the same dose and administer growth factors 2nd episode: administer ramucirumab as the same dose 3rd episode: definitive discontinuation of IMPs	Delay the cycle until absolute neutrophil count >1500/mm ³ . 1st episode administer tusamitamab rfvansine next cycle at the same dose and administer growth factors 2nd episode: administer tusamitamab rfvansine at reduced dose 3rd episode: definitive discontinuation	Follow ASCO guidelines on G-CSF usage and antibiotherapy. Repeat test every 3 days.

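### The neutropenia sentence in Protocol 6.6.4 has no grade, duration or drug and departs from Appendix 4, most firmly for Grade 4 febrile neutropenia, where 6.6.4 and 8.2.6.4 reduce one episode later

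*Protocol*

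**What the plan says.** Protocol Section 6.6.4 first says that "cycle delays and dose modifications should be implemented according to Appendix 4" and near its end points to the same appendix "for further guidance in dose modification or discontinuation". Between the two pointers it adds this rule: "neutropenia or febrile neutropenia, prophylactic G-CSF should be started and in case of second episode beside prophylactic G-CSF, then dose should be reduced".

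Appendix 4 (Protocol Section 10.4) works by grade, duration and drug:

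- **Grade 2 neutrophil count:** delay, then "Restart at the same dose" for both drugs. The supportive-care column asks for no intervention.
- **Grade 3, or Grade 4 outside the separate row for more than 7 days:** tusamitamab ravtansine restarts "at the same dose prophylactic G-CSF can be considered in all subsequent cycles". Ramucirumab also restarts unchanged, with G-CSF to be considered. Supportive care reads "Follow ASCO guidelines on usage G-CSF and antibiotherapy".
- **Grade 4 for more than 7 days:** same dose plus growth factors at the first episode. At the second, tusamitamab ravtansine is reduced, but for ramucirumab the entry is "2nd episode: administer ramucirumab as the same dose".
- **Grade 3 febrile:** same dose plus G-CSF at the first episode, both drugs reduced at the second.
- **Grade 4 febrile:** both drug columns open with Investigator's discretion. For tusamitamab ravtansine the cell then lists reduction with G-CSF at the first episode and definitive discontinuation at the second. Ramucirumab is left to the label.

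Section 8.2.6.4 limits prophylactic G-CSF to febrile Grade 3 or 4 events and Grade 4 counts lasting over a week. It reduces tusamitamab ravtansine on recurrence despite G-CSF, and stops treatment if the reactions persist at the lower dose.

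**The concern.** A site treating neutropenia can find two instructions for the same event. The 6.6.4 sentence is not idle text: Section 6.5.1 sends the reader to Section 6.6 for secondary G-CSF prophylaxis.

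Two things are at stake. After a first Grade 4 febrile episode, which Appendix 4 describes as life-threatening, 6.6.4 and 8.2.6.4 contain no dose step, so the next cycle could be given at full dose. At the mild end, a second Grade 2 or short Grade 3-4 episode could use up the only tusamitamab ravtansine reduction in Tables 11 and 12, and the reduced dose is then kept. Section 6.6.4 does add that a "second dose reduction may be needed, and need to be decided case by case discussion with the sponsor", so that limit is not absolute.

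**Working it through.** The plan states no figure to reproduce, so the check sets the texts side by side. The inputs are Protocol 6.6.4 (including Tables 11 and 12 and the text after them), 8.2.6.4 and Appendix 4.

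| Event | Appendix 4 | 6.6.4 taken literally | Result |
|---|---|---|---|
| Grade 2 | Same dose, no G-CSF, no reduction step | G-CSF started; reduction at second episode | Differ |
| Grade 3 or short Grade 4 | Same dose, G-CSF considered, no reduction step | As above | Differ |
| Grade 4 >7 days, tusamitamab ravtansine | Growth factors, then reduction at second episode | As above | Agree |
| Grade 4 >7 days, ramucirumab | Same dose at second episode | Reduction, if the unnamed dose includes ramucirumab | Ambiguous |
| Grade 3 febrile, both drugs | G-CSF, then reduction at second episode | As above | Agree |
| Grade 4 febrile, tusamitamab ravtansine | Discretion; reduction and G-CSF at first episode, stop at second | No dose step at first episode; reduction at second | Differ by one step |

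The rows do not carry equal weight. Appendix 4 numbers no episodes for Grade 2 or for Grade 3 and short Grade 4, so the difference there on dose is the absence of a reduction step, not an explicit second-episode instruction. The difference on G-CSF is direct for Grade 2 (started against no intervention) and softer for Grade 3 and short Grade 4 (started against considered).

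**Grade 4 febrile row, traced for a participant at the Tables 11 and 12 starting dose:**

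1. *Appendix 4 as listed.* First episode: tusamitamab ravtansine goes from 100 to 80 mg/m² Q2W, or from 150 to 120 mg/m² Q3W. Second episode: stop.
2. *Sections 6.6.4 and 8.2.6.4 alone.* First episode: G-CSF, dose still 100 or 150 mg/m². Second episode: 80 or 120 mg/m². Further reactions at that dose: stop.
3. *Reduction made at the first episode, then the body text.* Second episode: the text after Tables 11 and 12 requires discontinuation when an event would call for a further reduction, and 8.2.6.4 stops treatment for reactions at a lowered dose. This reaches the Appendix 4 endpoint.

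After the first episode, routes 1 and 2 differ by (100 − 80)/100 = 20% in the doublet cohort and (150 − 120)/150 = 20% in the triplet cohort. After the second, route 2 still gives a reduced dose where route 1 gives none.

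**The case against.** The best defence is that 6.6.4 already defers to Appendix 4 twice and ties adjustments to the worst grade in the cycle. The disputed sentence can then be read as a loose summary, with 8.2.6.4 supplying grades, duration and drug and itself citing the appendix. A careful site could resolve much of the difference this way, and modifications not stated in the protocol go to the Sponsor except for immediate safety. That tempers the point but does not remove it. No precedence rule settles two sections that disagree on one event: the instruction to take the most conservative adjustment covers several reactions in one participant. Section 8.2.6.4 also differs from Appendix 4 in the Grade 4 febrile row, so it cannot repair 6.6.4 there.

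A second defence is that the 6.6.4 reduction requires recurrence on prophylactic G-CSF. A Grade 2 participant managed by Appendix 4 never receives it, so the reduction is never triggered. This holds for a site already following Appendix 4. A site following 6.6.4 starts G-CSF at the first episode and so meets the condition at the second. For Grade 3 and short Grade 4, both texts lean on ASCO guidance that is not reproduced in the protocol, so how far starting and considering G-CSF differ in practice cannot be settled.

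A reader might infer that the protocol contradicts itself on ramucirumab in Grade 4 lasting more than 7 days. The documents do not show this. Section 6.6.4 names no drug and 8.2.6.4 names only tusamitamab ravtansine, so this is an ambiguity.

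**Conclusion.** The point holds as a wording conflict with a safety consequence. It is firmest for Grade 4 febrile neutropenia, where 6.6.4 and 8.2.6.4 place the first reduction one episode later than Appendix 4 lists it. That comparison is with a cell that opens with Investigator's discretion, so Appendix 4 is the listed course and not an absolute rule. For Grade 2 and for Grade 3 or short Grade 4 events, the conflict depends on taking the ungraded sentence literally.

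A reader might go further and conclude that the body text always allows re-dosing after a second Grade 4 febrile episode. It does not: if the first-episode reduction was made, the text after Tables 11 and 12 and Section 8.2.6.4 also lead to discontinuation. Re-dosing follows only if that reduction was skipped.

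The number of participants affected is unknown because the documents give no neutropenia rates. The 20% step is the size of the tabulated reduction, not an estimate of impact. No effect on DLTs, ORR or power is claimed.

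**What to change.** Replace the 6.6.4 sentence with: *For neutropenia or febrile neutropenia, follow the grade- and duration-specific rows of Appendix 4 for G-CSF and for the dose of each IMP.*

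Amend 8.2.6.4 so that Grade 4 febrile neutropenia follows Appendix 4: tusamitamab ravtansine reduced with G-CSF at the first episode and discontinued at the second, subject to the discretion stated there.

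The cost is one sentence replaced and one step aligned. No new data are needed, and endpoints, sample size and analyses do not change. SAP Section 1.1 records that the triplet cohort had not started, so for that cohort the change could be made before any dosing.

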6.6.2 Triplet cohort

If ≥ 2 of the first 3 patients or of the 6 patients treated at the initial DL present with DLTs, the SC may decide to decrease the dose of tusamitamab rfvantsine to DL -1 (120 mg/m² in combination with 10 mg/kg ramucirumab). The tolerability of the reduced DL will be assessed in at least 6 participants. Dose reduction in the case of 2 or more DLTs for the cohort is shown in [Table 10](#).

Table 10 - Dose reduction for triplet cohort

Dose level (DL)	tusamitamab rfvantsine	ramucirumab	pembrolizumab
Starting dose	150 mg/m ² Q3W	10 mg/kg Q3W	200 mg Q3W
Minus -1 (DL-1)	120 mg/m ² Q3W	10 mg/kg Q3W	200 mg Q3W

DL=dose level; Q3W=every 3 weeks.

Infusion of tusamitamab rfvantsine will be administered at least 1 hour after the end of ramucirumab infusion. For patients with a BSA >2.20 m², the tusamitamab rfvantsine dose will be calculated based on a BSA of 2.20 m².

6.6.3 Doublet cohort (Part 1 and Part 2) and triplet cohort: Requirements for retreatment

For the retreatment of patients on Day 1 of each subsequent cycle, the following conditions should be met:

- Neutrophils count $\geq 1.5 \times 10^9/L$.
- Platelets $\geq 100 \times 10^9/L$.
- Total bilirubin $\leq 1.5 \times ULN$.
- AST, ALT $\leq 2.5 \times ULN$ or $\leq 5 \times ULN$ in case of documented liver metastasis.
- No IMP-related toxicity Grade >1 (except for alopecia) or baseline severity.
- Urine protein:
 - $<2+$ on dipstick or urinalysis for C1D1,
 - $\leq 2+$ on dipstick or urinalysis for subsequent infusions,
 - OR
 - <2 g on 24 hours urine collection.
- Hypertension is controlled, every attempt should be made to control blood pressure (<140 mmHg systolic and <90 mmHg diastolic).
- Wound healing: any wound is fully healed.

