	Grade 3-4 Severe Eg, symptomatic bronchospasm, urticaria lesions covering $>30\%$ BSA, hypotension, angioedema.	Interrupt ramucirumab infusion and prematurely definitively discontinue ramucirumab	Interrupt tusamitamab rvtansine infusion and prematurely discontinue tusamitamab rvtansine and consider infusion delay.	Give diphenhydramine 50 mg IV and/or dexamethasone 10 mg IV and/or epinephrine and any required treatment per investigator judgement.
Ocular toxicity: Keratopathy/keratitis ^b associated with tusamitamab rvtansine	Grade 1 - Asymptomatic Corneal lesions only observed on routine ocular examination and not requiring topical treatment.	Administer ramucirumab at same dose, and same day as tusamitamab rvtansine	Next infusion of tusamitamab rvtansine at the same dose, with or without cycle delay, depending on the recommendation from the ophthalmologist (nature and extent of the lesion).	Standard ocular examination is planned as recommended by the ophthalmologist.
	Grade 2 Symptomatic or requiring topical treatment (curative) or limiting instrumental activity of daily life. Moderate decrease in visual acuity (best corrected visual acuity 20/40 and better or 3 lines or less decreased vision from known baseline)	Administer ramucirumab as planned, and re-introduce tusamitamab rvtansine when recovery to Grade 1	1 st episode: Omit tusamitamab rvtansine until resolution to Grade 1 (asymptomatic) and restart tusamitamab rvtansine at the same dose. 2 nd episode: Omit SAR until resolution to Grade 1 (asymptomatic) and tusamitamab rvtansine dose reduction. 3 rd episode: depending on benefit risk, premature definitive discontinuation of tusamitamab rvtansine may be envisaged	Standard ocular examination weekly until resolution ^{c, d} . Start curative treatment per ophthalmologist recommendation. After resuming study treatment, participant should be followed with standard ocular examination by every 2 cycles, even asymptomatic during next 4 cycles. If no recurrence, standard process with follow-up with ocular symptom is resumed. Management of study drug upon recurrence to be discussed according to Grade of the event at recurrence, clinical benefit from study drug and recommendation from the ophthalmologist.

Event	Symptoms severity (Nadir) (NCI CTCAE v5)	Management of IMP dosing (ramucirumab))	Management of IMP dosing (tusamitamab rvtansine)	Supportive care guidelines

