	Grade 3 Symptomatic with marked decrease in visual acuity (best corrected visual acuity worse than 20/40 or more than 3 lines of decreased vision from known baseline, up to 20/200); corneal ulcer; limiting selfcare activity of daily life	Administer ramucirumab as planned, and re-introduce tusamitamab rvtansine when recovery to Grade 1	1 st episode: Omit tusamitamab rvtansine until resolution (asymptomatic) and restart tusamitamab rvtansine with dose reduction. 2 nd episode: definitive discontinuation of tusamitamab rvtansine.	Standard ocular examination weekly until resolution ^{c, d} . Start curative treatment per ophthalmologist recommendation. After resuming study treatment, participant should be followed with standard ocular examination by every 2 cycles, even asymptomatic during next four cycles. If no recurrence, standard process with follow-up with ocular symptom is resumed Management of study drug upon recurrence to be discussed according to Grade of the event at recurrence, clinical benefit from study drug and recommendation from the ophthalmologist
	Grade 4 Perforation or best corrected visual acuity of 20/200 or worse in the affected eye.	Administer ramucirumab as planned,	Definitive discontinuation of tusamitamab rvtansine.	Complete the corneal examination as recommended by ophthalmologist. Repeat the standard ocular examination weekly ^c until resolution ^d . Start curative treatment per ophthalmologist recommendation.
Conduction disorder associated with tusamitamab rvtansine	Grade 1 Mild symptoms	Administer ramucirumab as planned,	tusamitamab rvtansine administration to be continued upon decision by the Investigator and Sponsor, depending on the nature of the conduction disorder.	ECG performed once weekly until event resolution. Additional evaluations such as LVEF and Holter monitoring should be performed when relevant.
	Grade ≥2	Administer ramucirumab as planned,	Definitive discontinuation of tusamitamab rvtansine.	ECG to be repeated twice weekly until event resolution. Prompt cardiology consultation Additional evaluations such LVEF and Holter monitoring should be performed when relevant.

Event	Symptoms severity (Nadir) (NCI CTCAE v5)	Management of IMP dosing (ramucirumab)	Management of IMP dosing (tusamitamab rfvansine)	Supportive care guidelines

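### Section 6.6.4 gives conflicting instructions on a second tusamitamab dose reduction, and its dose tables define no reduction step for a participant assigned to DL -1

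*Protocol*

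**What the plan says.** Protocol Section 6.6.4 addresses a further reduction in three places.

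- **Text before the tables.** "During the conduct of the study, second dose reduction may be needed, and need to be decided case by case discussion with the sponsor". No drug or cohort is named. The sentence before it concerns ramucirumab: "Approved product label should be followed for patient receiving ramucirumab treatment for supportive care and dose modification requirement due to not listed adverse events". The sentence after it introduces Tables 11 and 12, which cover all the study drugs.
- **Tables 11 and 12.** The second tusamitamab reduction is marked "not permitted" in both cohorts. Ramucirumab has a tabulated second reduction: 5 mg/kg Q2W in the doublet and 6 mg/kg Q3W in the triplet.
- **Text after the tables.** The limit is one tusamitamab reduction or two ramucirumab reductions. A patient at that limit whose event calls for an additional "dose reduction must be discontinued from tusamitamab" (the text continues with a slash and ramucirumab). No exception is given.

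Appendix 4 (Section 10.4), to which Section 6.6.4 refers sites, gives reduction instructions by event. For a first Grade 3 keratopathy episode, tusamitamab is omitted "until resolution (asymptomatic) and restart tusamitamab rvtansine with dose reduction". For Grade 2 keratopathy, a reduction comes at the second episode. At the third, "depending on benefit risk, premature definitive discontinuation of tusamitamab" is offered as an option.

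DL -1 is 80 mg/m² Q2W in the doublet (Section 6.6.1, Table 9) and 120 mg/m² Q3W in the triplet (Section 6.6.2, Table 10). Of that level, Section 6.6.2 says: "The tolerability of the reduced DL will be assessed in at least 6 participants". Section 4.1 allows DL -1 to become the recommended dose.

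**The concern.** The rule decides when tusamitamab is permanently stopped for toxicity. The text before the tables leaves a second reduction open to discussion. The cells and the sentence after them close it. An investigator relying on one part of Section 6.6.4 and an investigator relying on another would manage the same patient differently, and each could cite the protocol.

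The planned summaries would then mix two policies. SAP Section 4.7.1.2 reports tusamitamab dose reductions and relative dose intensity. SAP Section 4.2 and Table 9 report permanent partial discontinuation of tusamitamab. Differences in these figures could reflect how a site read the protocol rather than how the regimen was tolerated.

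The DL -1 gap is separate. That level opens only after excess DLTs, so instructions to reduce are likely to matter there. Yet the tables count steps only from the planned starting dose.

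**Working it through.** **1. The statements on a second reduction, side by side**

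| Source in Section 6.6.4 | Drug | Second reduction |
|---|---|---|
| Sentence before the tables | Not named | Possible, decided case by case with the sponsor |
| Tables 11 and 12 | Tusamitamab | Not allowed |
| Tables 11 and 12 | Ramucirumab | Tabulated dose |
| Sentence after the tables | Tusamitamab, after 1 reduction | Mandatory stop |

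If the first row covers tusamitamab, it contradicts the second and fourth rows. If it covers only ramucirumab, it adds a sponsor discussion to a step that the tables list without one, which is compatible with them. The text does not say which is meant.

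**2. Steps available in the tables**

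Relative step = (current dose − next dose) / current dose.

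- Tusamitamab from the starting dose: doublet (100 − 80)/100 = 20%; triplet (150 − 120)/150 = 20%.
- Tusamitamab from DL -1: the tabulated first reduction is 80 mg/m² in the doublet and 120 mg/m² in the triplet. These are the doses already assigned, so no lower step is listed.
- Ramucirumab: doublet (8 − 6)/8 = 25%, then (6 − 5)/6 = 16.7%; triplet (10 − 8)/10 = 20%, then (8 − 6)/8 = 25%.

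A participant assigned to DL -1 has had no individual reduction. The limit of one is therefore unused, so the mandatory-stop sentence does not plainly apply, and the tables offer nothing lower. An Appendix 4 instruction to reduce cannot be carried out from the tables.

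**3. How likely the DL -1 gap is to matter**

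The criterion in Section 4.1 is at least 2 DLTs in the first 3 or in 6 participants. Two or more in the first 3 also counts as two or more in 6, so for a true DLT rate p:

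P(criterion met) = 1 − (1 − p)^6 − 6p(1 − p)^5

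- p = 0.10: 1 − 0.53144 − 0.35429 = 0.11427, or 11.4%
- p = 0.20: 1 − 0.26214 − 0.39322 = 0.34464, or 34.5%
- p = 0.30: 1 − 0.11765 − 0.30253 = 0.57982, or 58.0%

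At p = 0.05 and p = 0.40 the values are 3.3% and 76.7%. The rates are assumptions; the documents give none for these combinations.

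**The case against.** The best defence is that the case-by-case sentence concerns ramucirumab. It follows a sentence about ramucirumab and names no drug. The tables fix the size of the second ramucirumab reduction without saying that it may be taken without discussion. This reading is possible, and a reader who concludes that the sentence cannot mean ramucirumab alone goes further than the text. What stands against the defence is that the sentence carries no such limit and leads straight into tables for every drug.

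A second defence is the general clause: "Dose modifications different from those stated in the protocol should be made only in consultation with the Sponsor unless required for immediate participant safety". It provides for departures from the protocol, but does not say which of two stated rules is the protocol's rule.

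Four stronger readings are tempting, and the documents do not support them.

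- **Appendix 4 as a third conflicting rule.** At the third Grade 2 keratopathy episode it prescribes no further reduction, so the trigger for the mandatory stop is not strictly met. The wording should be aligned with whatever rule is settled, but it is not a third outcome for the same event.
- **No lowering of exposure at DL -1.** Appendix 4 omits tusamitamab until recovery before any restart after Grade 2 or 3 keratopathy. The gap is an undefined step, not an absence of any action.
- **At least 6 participants affected per cohort, or all 30 in the efficacy analysis.** If 2 of the first 3 at DL -1 have DLTs, the cohort may stop there. The figure of 30 requires DL -1 to become the doublet's recommended dose. No document reports that DL -1 was opened.
- **Changed efficacy estimands.** ORR, DOR and PFS handle discontinuation by treatment policy (SAP Sections 4.3.2.2 and 4.4.2.2), and Part 2 tests no hypothesis.

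A reader may also ask whether the slash in the stopping sentence means both drugs. The protocol's next statement, that the remaining drug or drugs can continue, largely answers this.

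**Conclusion.** The point holds in two parts. First, Section 6.6.4 leaves open whether a second tusamitamab reduction is prohibited with a mandatory stop, or can be agreed with the sponsor. This applies in both cohorts, to any participant who has had one tusamitamab reduction. It rests on the text alone; its frequency cannot be estimated because the documents give no expected rate of reductions.

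Second, the tables define neither a lower step nor a consequence for a participant assigned to DL -1 who meets a reduction instruction. This is conditional on DL -1 being opened, for which the chance of meeting the criterion ranges from 3.3% to 76.7% over assumed DLT rates of 5% to 40%.

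The effect is on patient safety and on the consistency of the exposure and discontinuation summaries. Sample size and confidence-interval methods do not change. Observed response could still vary with the exposure actually given. SAP Table 6 has a low-dose class, at or below 72.5 mg/m², so a dose in that range would be classified. That class sorts doses received and authorises none. The SAP covers the doublet only.

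**What to change.** The sponsor should reconcile the passages so that one rule remains:

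1. In Section 6.6.4, reconcile the case-by-case sentence with the tusamitamab cells in Tables 11 and 12 and with the mandatory-stop sentence, naming the drug or drugs to which it applies.
2. Express the steps in Tables 11 and 12 relative to the participant's assigned dose level, and state what an Appendix 4 reduction instruction means for a participant assigned to DL -1.
3. Align the Appendix 4 text for the third Grade 2 keratopathy episode with the reconciled rule.
4. Check that the row labels in SAP Table 6 still match.

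The choice of rule and doses is the sponsor's; none is proposed here. The cost is amendment wording in Section 6.6.4 and Appendix 4 and, if needed, a label in the SAP. No extra data are required, since all changes to administration are already recorded in the eCRF. SAP Section 1.1 says the triplet cohort has not started, so there the correction can be in place before the first dose.
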